### 23. Inclusion/Exclusion Criteria:

#### Inclusion:

- Female
- Between 21 and 74 years old
- Menstruating for pre-menopausal and not menstruating for at least 6 months for the post-menopausal women. **The FDA defines postmenopausal as:** 12 months of spontaneous amenorrhea or 6 months of spontaneous amenorrhea with serum FSH levels >40mIU/ml or 6 weeks postsurgical bilateral oophorectomy with or without hysterectomy (U.S. Department of Health and Human Services, 2003).  
**Premenopausal is defined as** the period in a woman's life preceding menopause.
- DSM-5 diagnosis of hypoactive sexual desire disorder (HSDD) (also called disorder in sexual thoughts or interests)

#### Exclusion:

- Male
- < 21 years-old or > 74 years-old
- Hairstyles that induce artifacts to the EEG recording (i.e. braids, weave, extensions)
- Currently taking psychotropic medication
- Currently pregnant or lactating
- Women who report not being able to stop drinking alcohol during the duration of the study
- History of seizures or neurological disorders
- Under hormonal therapy
- Current or past diagnosis of cancer
- Any unstable medical illnesses
- Lifetime history of bipolar disorder, schizophrenia, or psychotic disorder
- Current or recent (past 3 months) substance abuse or dependence
- Current or recent (past 3 months) clinical depression
- Currently taking any medications that have/may have unfavorable interactions with Flibanserin
- Uncorrected vision
- Hepatic impairment

**24. Study Drug Compliance:**

In order to assess study drug compliance, we will ask subjects to bring back any unused medication at their next visit. Any missed doses will be accounted for by counting the number of pills the subject returns.

**25. Study Drug Dispensation:**

During the first visit, after [name] or [name] meet with the subject and determine if the subject is eligible to participate in the study, one of them will send a prescription to the investigational drug services (IDS) pharmacy at the University of Chicago Medical Center. The prescription is based on a randomization chart, so the physicians will order the drug by placing a coded patient number on the prescription sheet. When sent to the IDS pharmacy, they will know if that specific ID number is randomized to the flibanserin or the placebo, thus keeping it blinded to the physicians. Shortly after the study drug is ordered, a member of the study staff will pick it up from the IDS pharmacy and deliver it to the EEG lab where the subject will be doing the EEG procedures. After the subject is finished with all visit procedures, she will be given the study drug and instructions on how to take it.

All tablets will be dispensed at one time during the first visit. The total number of tablets each subject will receive is 56 tablets (8 weeks x 1 tablet/day).

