## **4. Primary Outcome Measure:**

EEG Results: Evoked Brain Potentials (measured brain response that is the direct result of a specific cognitive event). We will be analyzing change from baseline EEG results at 8 weeks (before and after the subject takes the flibanserin or placebo). We will average the electrical brain activity evoked by each type of stimuli to calculate the evoked brain potentials (any stereotyped electrophysiological response to a stimulus).

Evoked brain potentials in response to sexually desired stimuli compared to:

1. Non sexually desired stimuli
2. Basic visual non-sexual stimuli (reversal checkerboard) will be our proposed endpoints, as they will allow us to measure electric brain signals specific to cognitive

mechanisms underlying sexual stimuli processing rather than any other non-cognitive processes or basic visual processes. Amplitude of the signal, latency, and brain topography across 128 recorded vectors will be measured.

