Subjects will be recruited via Flyers posted on Campus and/or in Obstetrics and Gynecology practices and/or via ads posted on Craigslist by research coordinator, [name]. From these ads, interested individuals will be asked to go on Survey Monkey (<https://www.surveymonkey.com/r/HPENlabresearch>) and complete a survey that will help us determine whether they meet our selection criteria or email [name] at [[contact]](mailto:[contact]) or call the research team. Research coordinator will then contact individuals who may meet selection criteria. She and [name] and/or [name] will meet with them and give them the informed consent to read and go through it with the subjects. Upon receipt of a signed informed consent, participants will meet with [name] or [name] who will diagnose them with HSDD. If the subject does not have HSDD, she is not eligible to participate in the study. Subjects with a confirmed diagnosis of HSDD by [name] or [name] will then be randomly assigned by the UChicago Pharmacy/Investigational Drug Service to either Addyi (100 mg once daily at bedtime for 8 weeks, n = 60 subjects) or placebo (100 mg once daily at bedtime for 8 weeks, n = 60 subjects). The research question of this double-blind randomized outpatient clinical trial is to determine the pre-post change in the Flibanserin group and investigate the

extent to which Flibanserin normalizes brain activity in women with HSDD and the extent to which regional brain activation is associated with changes in symptoms and behavior (as measured with self-report measures of sexual desire and/or eye-tracking movements).

The study is registered on clinicaltrials.gov.

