## **6. Duration of Protocol:**

The total duration of the entire study on campus is 4.5 hours maximum. **Visit 1's duration:** 2 hours. Upon receipt of the subject's written consent, the subject will meet with [name] or [name] to have a diagnosis of HSDD confirmed, take a urine pregnancy test, and be asked to fill out questionnaires (duration 45 minutes maximum). Then, an IRB-approved member of the HPEN laboratory will walk the subject to the laboratory where the subject will be completing other questionnaires and performing the behavioral visual task while the subject's brain activity and eye movements are recorded (1h15 minutes maximum, including breaks and time to walk to the laboratory). At the end of Visit 1, a member of the HPEN laboratory will walk the subject to the pharmacy where they will receive either Flibanserin or Placebo. The HPEN member will not know what the patient receives (placebo or Flibanserin). One week after visit 1, a member of the study staff will contact the subject via telephone to see if the subject has experienced any side effects or if the subject has any questions. If any side effects are reported, the study staff will immediately contact [name] or [name] to confirm that any appropriate follow up is provided. **Phone call 2's duration:** 30 minutes. Two weeks after visit 1, the subject will be asked about any side effects she has experienced or is currently experiencing. The subject will also be asked to fill out some of the same questionnaires as visit 1 and answer questions about mood and sexual desire. **Visit 2's duration:** 1 hour. The subject will go directly to the HPEN laboratory, where the subject will perform the behavioral visual task again while the subject's brain activity and eye movements are recorded and fill out the same questionnaires the subject filled out during Visit 1. **Visit 3's duration:** 1 hour. The subject will again go directly to the HPEN laboratory to perform the behavioral visual task while the subject's brain activity and eye movements are recorded and fill out the same questionnaires as Visits 1 and 3.

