## **10. Type and Number of Experimental Subjects:**

We expect to collect data from a total of 120 subjects between the age of 21 and 74 years. We will be testing premenopausal and postmenopausal women with hypoactive sexual desire disorder. Flibanserin is FDA approved for premenopausal but not postmenopausal women with HSDD. Women who are pregnant (or think they are pregnant), or who are nursing (or breastfeeding), or women who report not being able to stop drinking alcohol during the duration of the study will NOT be tested.

**Power:** Using G\* power calculation software (Version 3.1.9.2) for a within-between interaction in repeated measures ANOVA, a total sample size of 120 will yield 95% power to detect a significance, with alpha = .05 and an effect size of 0.14.

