and mechanism of missing data. A 2 (Treatment Type: Addyi or Placebo) x 2 (Group Type: pre- or post-menopausal) X 2 (type of stimuli: desired, nondesired) x 3 time (Visit 1, Visit 2, Visit 3) repeated-measures ANOVA will be performed on the reaction times and ratings to assess for main effects and interaction effects. P values, confidence interval, and effect sizes will be reported.

iii. Eye-tracking Data: A similar ANOVA will be performed for the following dependent variables: onset to first fixation and duration of fixation. As in our 2014's paper (Bolmont, Cacioppo, & Cacioppo), we will also analyzed include the subjects' visual area of interest (face vs. body) as a within-subject factors in our ANOVA.

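### Allocation is not conditional on a usable baseline EEG, and hair is required to be EEG-compatible only at entry, so some primary change scores may be lost avoidably after randomisation

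*Combined protocol and SAP*

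**What the plan says.** **Order of events.** Section 5 has the pharmacy assign women at random once HSDD is confirmed; no EEG condition is attached. In Section 25 the physician decides eligibility and then sends a prescription bearing a coded number that the pharmacy reads against the randomisation chart. Next: "Shortly after the study drug is ordered, a member of the study staff will pick it up from the IDS pharmacy". The drug is taken to the EEG laboratory, where the recording is still to come, and the woman receives it once the visit's procedures are finished.

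**A second account.** Section 6 places the physician's step first and the laboratory second, and then says: "At the end of Visit 1, a member of the HPEN laboratory will walk the subject to the pharmacy". It does not say when the prescription is ordered or the number used.

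**Hair.** Section 23 excludes "Hairstyles that induce artifacts to the EEG recording (i.e. braids, weave, extensions". EEG is also recorded at week 4 and week 8 (Sections 5 and 6), but no available passage mentions hair at those visits.

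**Outcome and sample size.** Section 4 defines the primary outcome on evoked potentials: "We will be analyzing change from baseline EEG results at 8 weeks". Section 10 states that "a total sample size of 120 will yield 95% power to detect a significance, with alpha = .05 and an effect size of 0.14"; the same 120 is the number of women expected to provide data, with no allowance for loss.

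**Missing data.** The intent-to-treat sentence in Section 11 concerns women who do not follow the dosing regimen. Examination of missing data is planned for the demographic, self-report and behavioural data. The electrophysiological paragraph has no such step and no rule for an unusable recording.

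**The concern.** A change score needs a usable recording at both ends. The plan commits a randomisation number before anyone has seen the first recording. If that recording fails, the trial has a randomised woman who must be re-recorded before dosing (not provided for), left out after randomisation, or kept in the intent-to-treat set without a primary outcome. The plan does not say which.

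The week 8 end is exposed in a different way. The sponsor treats certain hairstyles as enough of a threat to the recording to exclude women who wear them, yet hairstyles change over eight weeks. Alcohol is handled more fully: Section 23 has an entry exclusion and Section 12 an eight-week commitment. Hair has only the entry exclusion.

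At stake is precision on the primary outcome, in a design whose stated power leaves no room for lost recordings.

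**Working it through.** **1. Is the recording before or after allocation?**

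| Source | Step that triggers assignment or order | EEG required first? |
|---|---|---|
| Section 5 | Confirmed HSDD diagnosis | No |
| Section 9 | HSDD determined at Visit 1, then assignment | No |
| Section 25 | Physician finds the woman eligible | No; EEG follows delivery of drug to the laboratory |
| Section 6 | Not stated; pharmacy visit at the end of Visit 1 | Not stated |

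Three sections put assignment or the order after the clinical decision without requiring a recording, and Section 25 places the EEG later. Section 6 differs on who collects the drug and where, but is silent on the time of the order.

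**2. The plan's own power figure.** Inputs from Section 10: N = 120, alpha 0.05, effect size 0.14 (taken as Cohen's f), test a "within-between interaction in repeated measures ANOVA". Groups, measurements, correlation and sphericity are not stated. The only full design in the plan, written for the behavioural data, is "2 (Treatment Type: Addyi or Placebo) x 2 (Group Type: pre- or post-menopausal) X 2 (type of stimuli: desired, nondesired) x 3 time". That gives k = 4 groups and m = 6 measurements. Assume correlation rho = 0.5 and sphericity (epsilon = 1).

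- Noncentrality: lambda = f² × N × m / (1 − rho) = 0.0196 × 120 × 6 / 0.5 = 28.2
- df1 = (k − 1)(m − 1) = 3 × 5 = 15
- df2 = (N − k)(m − 1) = 116 × 5 = 580
- Power = 94.8%, which agrees with the stated 95%

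The agreement depends on the assumed settings. At rho = 0.5, 2 groups × 3 measurements gives 92.7%, 2 × 2 gives 86.0% and 4 × 3 gives 80.4%.

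**3. Women without a change score.** The documents give no rate of unusable EEG. Assume 5% to 10% from any cause at Visit 1 or week 8: 0.05 × 120 = 6 and 0.10 × 120 = 12.

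**4. Precision.** Section 5 gives 60 per arm: "Addyi (100 mg once daily at bedtime for 8 weeks, n = 60 subjects", with the same number on placebo. With equal loss in both arms and complete cases analysed, the standard error of the arm difference rises by the factor sqrt(60 / n remaining per arm):

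- 5% loss: sqrt(60/57) = 1.026
- 10% loss: sqrt(60/54) = 1.054

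**5. Power under the same loss (rho = 0.5).**

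| Settings | N = 120 | N = 114 (5%) | N = 108 (10%) |
|---|---|---|---|
| 4 groups × 6 measurements | 94.8% | 93.4% | 91.7% |
| 2 × 3 | 92.7% | 91.3% | 89.7% |
| 2 × 2 | 86.0% | 84.2% | 82.2% |

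The fall at 10% is 3 to 4 points whichever settings apply. This is the effect of all unusable EEGs. The share due to ordering before the recording, or to a changed hairstyle, cannot be found from the documents.

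**The case against.** **The exclusion can be checked in time.** A reader might infer that the hairstyle criterion is not secured before allocation. The documents do not support that. The criterion names hairstyles that can be seen without an EEG, candidates complete a survey on the selection criteria beforehand (Section 5), and eligibility is decided before the order (Section 25). This objection stands. What is unsecured is a technically usable recording, which is a different matter.

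**Bias is not shown.** Section 25 withholds the drug until the visit's procedures are done, and those doing the recording do not know the arm. A baseline failure therefore precedes dosing and should be unrelated to arm; nor does a later change of hairstyle have an evident link to arm. This also stands.

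**A failed baseline could be repeated.** No passage forbids a second recording before the first dose, so loss is possible, not certain. But no passage provides for one either, so the gap remains.

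**Women with braids are not permanently barred.** That reading is tempting, but the text does not say it; it only states no option to reschedule.

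**Section 6 does not settle the sequence.** It might be read as placing the order after the EEG. It describes collection only, so ordering after the recording would be a change to the plan.

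**The silence on hair is not fully verifiable.** Sections 7 and 19 and the consent form were not in the available text. The statement holds for the remainder.

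**Conclusion.** The point holds as a cheap improvement to protect the primary outcome. In Sections 5 and 25 the randomisation number is used before the baseline EEG, and in the available text hair compatibility is required only at entry. Some randomised women may therefore have no primary change score for reasons that could have been prevented.

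The size is modest and assumed: at 5% to 10% unusable EEG from any cause, 6 to 12 women lack a change score and the standard error rises by about 3% to 5%. Only an unknown part of that is due to the ordering sequence or hair. These figures rest on equal loss by arm and a complete-case analysis; the power figures also rest on the settings inferred for the plan's calculation. A reader should not conclude that the treatment comparison is biased or that such losses are bound to occur.

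**What to change.** 1. **Section 25:** release the coded prescription only after the Visit 1 EEG has been recorded and the EEG laboratory has confirmed it usable. State briefly what counts as usable and who judges it. Bring Section 5 into line, and reconcile the accounts of drug collection in Sections 6 and 25.
2. **Section 23:** replace the hairstyle exclusion with a requirement that the woman be able and willing to attend Visits 1, 2 and 3 with hair that permits EEG recording. State that Visit 1 may be rescheduled for this reason, and give a reminder when Visits 2 and 3 are booked.

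**Cost:** rewording of a few sections, a short wait for dispensing at the end of Visit 1, a message from the laboratory back to the physician, and a small commitment from participants. No additional visit is needed unless Visit 1 is rescheduled. The change removes the Visit 1 part of the loss from the randomised set and should reduce the hair-related part at weeks 4 and 8; it does not prevent unusable recordings from other causes at those visits.

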**26. Institutional Review Board (IRB):**

The supervisory role of the IRB includes reviewing, approving, and monitoring all aspects of this research. All changes that are made to the study are always approved by the IRB before being implemented. The University of Chicago IRB follows the ethical principles consistent with the Declaration of Helsinki of the World Health Organization and the Belmont Report. It follows the policies of the FDA, the protection of human subjects, and others. Please follow link to read more:

<http://bsdirb.bsd.uchicago.edu/policies-procedures/index.html>

**27. Prohibited Medications**

<http://www.fda.gov/Drugs/DevelopmentApprovalProcess/DevelopmentResources/DrugInteractionsLabeling/ucm093664.htm> (refer to section 12 for more information)

The following medications are not to be taken by eligible subjects:

atazanavir; azamulin; buspirone; Clarithromycin; darunavir; dextromethorphan N-demethylation; digoxin; eletriptan; erythromycin N-demethylation; felodipine; indinavir; itraconazole; ketoconazole; lopinavir; lovastatin; midazolam 1-hydroxylation; midazolam; nefazodone; nelfinavir; nifedipine oxidation; Nootkatone; rifampin; ritonavir; saquinavir; sildenafil; simvastatin; telithromycin; terfenadine C-hydroxylation; testosterone 6 b –hydroxylation; ticlopidine; tipranavir; triazolam 4-hydroxylation triazolam; troleandomycin; verapamil.

## **28. Adverse Events:**

[name], [name], and [name] will be responsible for the detection, documentation, classification, reporting, and follow-up of adverse events, including events meeting the definition of a serious adverse event (SAE). An adverse event (AE) us any undesirable experience associated with the use of a medical product in a patient. For the regulatory definitions of SAEs, refer to

<http://www.fda.gov/Safety/MedWatch/HowToReport/ucm053087.htm>.

All AEs will be recorded regardless of causality or severity. At the minimum, information collected concerning AEs should include the following: onset date, resolution date, severity (i.e., mild, moderate, or severe), relationship to study drug, intervention (if needed), seriousness of the event, and outcome.
